4.5. Sensitivity Analysis

The primary efficacy analysis will be repeated under 3 different scenarios as follows.

- (1) Randomization was stratified on two factors: (1) Bipolar or Major Depressive Disorder diagnosis, and (2) prior history of suicide attempt. Cox Regression Model as described in section 4.3 will be refitted with the inclusion of diagnosis variable and suicide history variable in the model.
- (2) Primary efficacy analysis will be repeated on the “per-Protocol” sample with adherence as defined in section 3.4 to evaluate efficacy among those adherent to the protocol.
- (3) Primary efficacy analysis will be repeated on the modified ITT analytic cohort that excludes all randomized subjects who terminated prior to the first titration visit.

4.6. Handling of Missing Data in Primary Analysis

Up to 40% of subjects have been estimated to drop out over the course of follow up prior to end of study at 12 months after randomization. To account for complete data loss from attrition, evaluable sample size has been inflated by 20% accordingly. Distribution of subjects lost to follow-up and missing data on key variables across the treatment groups will be monitored throughout the study.

All those who terminated early will be censored at the date of last visit or last contact and their time in the study from randomization to termination date will be considered in the primary analysis.

The primary analysis assumes that data are missing at random. This assumption will be tested by evaluating the distribution of missing data across the two treatment groups. Additionally, a Bayesian sensitivity analysis utilizing Pattern Mixture Modelling approach will be performed to determine potential bias in inference from all possible non-random patterns of missing data. (Rybin et. al., 2015)

5. Analysis Plan for Secondary Objectives

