To be conservative, our sample size estimate is based on an initial estimate of a 43% effect, the weighted average of the 48% reduction effect observed in the Lauterbach study and the 33% reduction effect observed in the Oquendo study. We adjusted for a potential attenuation of the effect due to non-adherence; estimating 15% non-adherence leads to a final estimated effect size of 37%. As discussed below, correction for the loss of data from patients who dropout is addressed through estimates of the sample size requirement, not the effect size for the intervention.

Missing Data from Attrition

In randomized clinical trials, Lauterbach (2008) and Oquendo (2011) reported overall attrition rates of 58% and 50% in the lithium group respectively, of which 21% and 11% were treatment related. Moreover, Lauterbach reported a similar rate of attrition for the placebo group, suggesting that there was no differential dropout.

The proposed study, unlike the previous trials, allows for continued enrollment of subjects who discontinue study medications. The sample size calculations are based on a dropout rate during the course of the study of approximately 40%, or assuming that the dropout rate is uniform, a reduction in the effective sample size of approximately 20%. Allowing for up to 40% dropout or approximately a 20% loss of data for reasons unrelated to treatment, the statistical power calculation is based on an effective sample size of 1,490 evaluable patients from a total of 1,862 enrolled. For the primary time to event analysis, we will censor follow up at the first occurrence of the primary endpoint event, death, or withdrawal from the study for any reason.

We will test the missing at random assumption using a Bayesian Pattern Mixture Missingness approach (Rybin et al., 2013), to validate the results and identify potential bias from possible non-random patterns of missing data. For secondary longitudinal analyses, we will evaluate missingness patterns and perform sensitivity analysis based on multiple imputation methods.

Non-Adherence to Study Protocol

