At the end of the study period, we will perform an electronic data sweep to collect passive follow-up data on lithium use and suicide related behaviors following active participation in the study for all subjects that had been randomized. In addition, death rates for individuals who were considered as part of pre-screening activities will be obtained by linking SSN with SPAN, BIRLS and the National Death Index. By the end of the 4 year study period, average follow-up including both active and passive follow up for the study subjects will be 2.5 years (first subject enrolled will have 4 years of follow up and last subject enrolled will have 1 year of follow up). However, subjects terminated from the protocol before they completed a full year of participation will have somewhat longer periods of passive follow-up. Data on lithium use and clinical and administrative data related to primary study endpoints over the extended observation period will be obtained by linking the study database to SPAN data, VA Electronic Medical Records data, VA Pharmacy Benefit Management data, the VA Beneficiary Identification and Records Locator System database, and the VA-DoD data repository for suicide-related data that will include data on causes of death from the National Death Index. Linkage for most variables will be through the VHA Corporate Data Warehouse, a national repository of data from VA Electronic Medical Records and several other VHA clinical and administrative systems.

Hospital admission records and discharge summaries will be collected to determine if a subject was hospitalized to prevent suicide.

XV. MONITORING ADVERSE EVENTS

Role of the Site Investigator and Research Team in Adverse Event Monitoring

The site Research Team is responsible for the following:

1. Closely monitoring all subjects for new adverse events (AEs) and/or serious adverse events (SAEs);
2. Reviewing accuracy and completeness of all AEs and/or SAEs reports.

3. Complying with Cooperative Studies Program policies for reporting AEs and/or SAEs.
4. Complying with local Research & Development Committee (R&DC) policies for reporting AEs and/or Serious AEs.
5. Complying with:
 - a. VA Central IRB (<http://www.research.va.gov/vacentralirb/>)
 - b. VHA Handbook 1058.01 Research Reporting Compliance Requirements
6. Notifying VA Central IRB and local R&DC of safety issues reported to the investigator by the CSP.

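### SAP 4.6 proposes to test missing at random by comparing missing data between arms, which cannot test it, and the pattern-mixture analysis that could show sensitivity has no stated range or tipping point

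*SAP*

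**What the plan says.** SAP 4.6 states: "The primary analysis assumes that data are missing at random". On early leavers it says: "All those who terminated early will be censored at the date of last visit or last contact". It then gives two checks. The first is: "This assumption will be tested by evaluating the distribution of missing data across the two treatment groups". The second follows at once, with no condition attached: "Additionally, a Bayesian sensitivity analysis utilizing Pattern Mixture Modelling approach will be performed to determine potential bias in inference from all possible non-random patterns".

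Protocol section VII (Missing Data from Attrition) has no between-arm comparison. It says: "We will test the missing at random assumption using a Bayesian Pattern Mixture Missingness approach", and gives the purpose as "to validate the results and identify potential bias from possible non-random patterns of missing data".

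Neither document gives priors, sensitivity parameters, a range of departures, a tipping point or a decision rule for the pattern-mixture analysis. The SAP cites a methods paper on missing data in a schizophrenia study. I have not seen that paper, and neither document says which of its settings would be used here.

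On data after exit, Protocol XIV (Extended Follow-up) says "we will perform an electronic data sweep to collect passive follow-up data on lithium use and suicide related behaviors" for everyone randomised. SAP 6.1 to 6.3 assigns those data to tertiary objective 2, which uses the primary endpoint and the primary analytic strategy. SAP 4.6 does not mention them.

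**The concern.** For the log-rank and Cox analyses, MAR amounts to non-informative censoring: within an arm, people censored at a given time must have the same later hazard as those who stay. The later hazard of leavers is not observed, so a count of how many left each arm says nothing about it.

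The protocol's own Table 2 shows how totals can mislead. In the earlier placebo-controlled lithium trial, overall attrition was 58% on lithium and 59% on placebo, while treatment-related attrition was 21% and 6%. Protocol VII takes the similar totals as a sign that dropout was not differential.

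Informative exit is plausible here. Protocol XII (Discontinuation and Withdrawal) says suicide-related behaviour may be more frequent in the first year after stopping lithium. Protocol XIII withdraws a participant whose provider decides that open lithium is essential, so worsening patients in either arm could leave. With up to 40% leaving, the HR among those still observed may differ from the HR for all randomised patients over 12 months.

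**Working it through.** **Inputs from the documents.** One-year event rates 15% and 9.45%, HR 0.61, 745 evaluable per arm, 182 events, final two-sided level 4.8% (SAP 4.3 and 10). Up to 40% dropout, counted as 20% data loss (SAP 4.6 and 10). 931 randomised per arm (Protocol VII).

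**Reproducing the plan.**
- HR = ln(1 − 0.0945)/ln(1 − 0.15) = 0.0993/0.1625 = 0.611.
- Events = 745 × (0.15 + 0.0945) = 182.
- Power with 182 events at the 4.8% level is 91.3% (Schoenfeld) or 90.2% (Freedman), against 90% stated.
- 1490/0.8 = 1863, against 1862 stated.

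The design figures hold.

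**Illustration 1: same dropout, different unseen hazards.** Assume a fraction d = 0.4 of each arm has an exit time u uniform over the year, a constant hazard λ before exit and mλ after it. The 12-month risk is

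r(m) = (1 − d)(1 − e^(−λ)) + d ∫₀¹ [1 − e^(−λu − mλ(1−u))] du,

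and the all-patient HR is ln(1 − r_Li)/ln(1 − r_Pl). As a rough check, 20% of person-time falls after exit, so an arm's cumulative hazard scales by about 0.8 + 0.2m. Doubling on lithium only gives 0.611 × 1.2 = 0.733.

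| m, lithium leavers | m, placebo leavers | Lithium risk | Placebo risk | 12-month HR |
|---|---|---|---|---|
| 1 | 1 | 9.45% | 15.0% | 0.61 |
| 1.64 (reversion to placebo hazard, 1/0.611) | 1 | 10.6% | 15.0% | 0.69 |
| 2 | 1 | 11.2% | 15.0% | 0.73 |
| 3 | 1 | 12.8% | 15.0% | 0.84 |
| 2 | 2 | 11.2% | 17.6% | 0.61 |
| 1 | 2 | 9.45% | 17.6% | 0.51 |

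The multiplier acts only after exit, so the between-arm comparison of missing data is the same in every row.

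**Tipping point for this example.** Vary lithium leavers only and suppose all 931 per arm are ascertained to 12 months. Then z ≈ −ln(HR) × √E / 2, with E = 931 × (r_Li + r_Pl).
- m = 1: E = 228, z = 3.7.
- m = 2: E = 244, z = 2.5.
- m = 3: E = 259, z = 1.4.

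The 4.8% critical value is 1.98. It is crossed at m of about 2.4 (HR about 0.78). The HR reaches 1.0 at m of about 4.4.

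**Illustration 2: does the arm comparison detect the problem?** Simulation with 931 per arm and 3000 runs per scenario. In the informative scenario, half the patients have four times the hazard of the other half. On lithium, 60% of high-risk and 20% of low-risk patients are given an exit time; on placebo these are reversed.

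| Scenario | True HR | Observed dropout, Li vs Pl | Estimated HR | Balance test p < 0.05 |
|---|---|---|---|---|
| Informative, opposite in the two arms | 1.00 | 36.0% vs 37.8% | 0.86 | 13% of runs |
| Informative, opposite in the two arms | 0.61 | 37.5% vs 37.8% | 0.53 | 5% of runs |
| Non-informative, unequal | 1.00 | 46.1% vs 27.7% | 1.00 | 100% of runs |

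In the first row the trial falsely favours lithium in 19.4% of runs, against a nominal 2.4%. In the third row the estimate is unbiased, yet the comparison rejects every time. When high-risk patients leave more often in the same way in both arms, the estimates are 1.00 and 0.615 for true HRs of 1.00 and 0.61, so informative dropout need not bias the HR. Balance is neither necessary nor sufficient.

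**The case against.** The strongest reply is that the arm comparison is only one of two checks. The pattern-mixture analysis is promised whatever the comparison shows, and both documents aim it at non-random missingness. A delta-adjusted analysis is itself a pattern-mixture analysis, so much of the remedy is already planned. This stands. A reader might infer that balanced dropout will be taken as validating the HR, but no sentence in either document says so. What remains is that the analysis is unspecified, that "to determine potential bias in inference from all possible non-random patterns of missing data" promises more than any model can deliver, and that the protocol still calls the method a test.

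A reader might also infer that censoring leavers favours lithium. The documents do not settle the direction. Protocol XII says the data cannot separate unmasking from withdrawal, and that gradual discontinuation may lessen the increase; tapering is planned. In the table above, doubling in placebo leavers only moves the HR to 0.51, which means censoring would understate the benefit. Doubling or tripling on lithium alone puts leavers at 1.22 or 1.83 times the placebo hazard (2 × 0.61 and 3 × 0.61), which is rebound harm and more than loss of benefit.

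Stopping the drug is not leaving the study. Protocol XIV and Table 7 keep discontinuers under assessment if they agree, and 40% is an upper planning figure. This limits the problem to those who leave follow-up.

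Finally, tertiary objective 2 already analyses post-exit events in the primary manner. It does not fill the gap. It runs to the end of the study period, past the 12-month handoff at which treatment is unblinded and placebo patients may start lithium (Protocol V and XIV), so it answers a different question.

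**Conclusion.** The between-arm comparison in SAP 4.6 cannot do what the SAP assigns to it, and the wording should change. The pattern-mixture analysis is the right kind of tool but needs stated departures before it can inform the reading of the primary result.

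On the assumptions shown (40% uniform exit in both arms, constant hazards, observed HR 0.61), the 12-month all-patient HR lies between about 0.51 and 0.73 for a doubling of post-exit hazard in one arm only, and is 0.69 for simple reversion to the placebo hazard. The multipliers, the uniform exit times and the simulated risk classes are assumptions chosen to show possible size. They do not estimate the bias in this trial, and its direction is unknown. The primary test, significance level and sample size are unaffected.

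**What to change.** 1. In SAP 4.6, replace the test with a descriptive report of dropout by arm, timing and reason. State that MAR cannot be tested from the observed data, and remove the claim to cover every non-random pattern. Bring Protocol VII into line, since it also speaks of testing MAR.

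2. Specify the planned pattern-mixture analysis: separate post-dropout hazard multipliers for lithium and placebo leavers, a stated range for each (or priors, if it stays Bayesian), and the combinations at which significance at the 4.8% level is lost.

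3. Add a sensitivity analysis of the primary endpoint cut at 12 months from randomisation. For early leavers, use the electronic sources already planned for tertiary objective 2 and in Protocol XIV (SPAN, medical record, death index). Exclude data after consent withdrawal, when Protocol XIV stops collection, and after HIPAA revocation, when SAP 3.3 ends inclusion.

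The cost is SAP wording and a little more analysis on data already to be collected. The limitation is completeness: registry events are captured less fully than adjudicated study events, and Protocol VIII says facilities know of somewhat less than half of suicide deaths. Item 3 should therefore be read beside item 2 and not in place of it.

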5.1. Secondary Objective

This trial has 5 secondary objects, which are described below. Analyses for these objectives are exploratory in nature and as such, they are not statistically powered for formal hypothesis testing. These objectives are to:

- 1) explore the effectiveness of lithium augmentation of enhanced suicide prevention management in preventing separately:
 - a. all-cause mortality
 - b. impulsive suicide reattempts
 - c. non-impulsive suicide reattempt
 - d. non-suicidal self-directed violence
- 2) explore heterogeneity of response to treatment subgroups including:
 - a. categories of age, race/ethnicity, and gender
 - b. diagnosis of depression vs. bipolar disorder
 - c. impulsive index attempt vs. non-impulsive index attempt
 - d. substance use vs. absence of substance use
 - e. individuals with and without trait impulsivity
 - f. individuals with and without trait aggression
 - g. subjects who have vs. have not received evidence based psychotherapies
- 3) explore the effect of lithium augmentation of enhanced suicide prevention management on total occurrence of all event types and cumulative occurrence of individual event type as follows:
 - a. all suicide attempts
 - b. all hospitalizations for prevention of suicide attempts
 - c. all self-directed violence
 - d. all emergency department visits

- 4) explore longitudinally the effect of lithium augmentation of enhanced suicide prevention management on symptoms of bipolar disorder and depression and suicidal ideation
- 5) explore mediators of the effect of lithium augmentation on prevention of suicide reattempt, specifically improved control of symptoms and lithium plasma levels

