In addition to repeated episodes of suicidal self-directed violence, the study will obtain data on a number of secondary outcomes within the 12 month follow up period. These will go beyond the time to the first outcome event to include the total numbers of suicide attempts, interrupted attempts, hospitalizations for the prevention of suicide, emergency department visits, non-suicidal self-directed violent behaviors, and deaths from suicide, unnatural deaths, and all-causes. To support exploratory analyses on subtypes of suicide attempts, the study will obtain data on impulsive and non-impulsive attempts.

Following the total number of suicide attempts and time to the first attempt will allow comparison of our findings with other studies that used rates of attempts as an outcome. Following the impact of the study treatment on other forms of self-directed violence will allow us to explore the specificity of the observed treatment effects. The proposal to evaluate treatment effects on all unnatural deaths and on all-cause mortality follows from concerns that deaths from other causes in patients who have survived suicide attempts may represent suicide-equivalents or cases misclassified by medical examiners or coroners. However, we recognize that the observed rates of all-cause of mortality in persons who have attempted suicide are lower than reattempt rates, and, therefore, the study would not be powered to detect a treatment effect on overall mortality. Finally, exploratory analyses on impulsive versus non-impulsive attempts, defined on the basis of reports of the absence or presence of premeditation on the Suicide Intent Scale, may provide further insights into whether any observed effects of lithium could be related to a decrease in impulsive behaviors.

Covariates

Measures of potential effect modifiers will include traits of impulsivity and aggression. Measures of potential mediators will include symptoms of the patients' affective disorders (including suicidal ideation).

VII. BIOSTATISTICAL CONSIDERATIONS

Overview

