Psychiatric Diagnosis	Mini-International Neuropsychiatric Interview (Sheehan et al., 1998)	MINI	Structured interview to elicit psychiatric symptoms and determine diagnoses	Interview	Variable	Eligibility	20
	PTSD Checklist (modified to allow DSM-IV-TR and DSM-5 diagnoses); Blanchard et al., 1996)	PCL	Self-rating scale to be administered as a structured interview	Self or Interview	22	Potential covariate for exploratory analyses	6
	Substance use disorders module from Structured Clinical Interview for DSM-IV-TR Axis I Disorders (First et al., 2002)	SCID SUD	Supplementary questions related to substance use diagnoses	Interview	Variable	Eligibility	10
Cognition and Decision-Making Capacity	Orientation Memory Concentration Test (Katzman et al., 1983)	OMC	Cognitive screening instrument	Interview	6	Eligibility	6
	The Jeste Decision-Making Capacity Assessment – University of California, San Diego Brief Assessment of Capacity to Consent (UBACC)	UBACC	Evaluation of decision-making capacity	Interview	Variable	Eligibility	5

[name]: CSP#590 Lithium for the Prevention of Recurrent Suicide Attempts

Mental Health Symptoms	Patient Health Questionnaire-9 (Kroenke et al., 2001)	PHQ-9	Symptoms of depression	Self or Interview	10	Secondary Outcome	7.5
	Internal State Scale (Bauer et al., 2000)	ISS	Symptoms of bipolar disorder	Self or Interview	15	Secondary Outcome	7.5
	Alcohol Use Disorders Identification Test-C (Bradley et al., 2007)	Audit C	Quantity-frequency data on alcohol use	Interview	3	Secondary Outcome	3
Moderators	Buss-Perry Aggression Scale (Buss & Perry, 1992)	Buss Perry	Aggression as a trait	Self	29	Secondary Outcome	10
	Barratt Impulsiveness Scale (Patton et al., 1995)	Barratt	Impulsivity as a trait	Self	30	Secondary Outcome	10
Lithium side effects	Lithium side effects checklist		Systematic review of possible lithium side effects	Interview	8	Monitoring	5
Use of VA and non-VA health and mental health services (Sirey et al., 2005)	Self-report log based on the Cornell Services Index (Sirey et al., 2005)		Use of health and mental health services to include patient's report of reasons for hospitalization or emergency department visits	Log maintained by subject and reviewed by research staff at each visit	Variable	Monitoring	5 minutes for review

Table 2: Comparison of select prior studies of lithium with CSP590

	Cipriani (2005)	Guzzetta (2007)	Goodwin (2003)	Lauterbach (2008)	Oquendo (2011)	Proposed CSP590

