5.3. Statistical Methods for Secondary Analyses

Secondary objective#1 will use a time to event, survival analysis to determine whether there is a treatment difference in event rates for each of the defined endpoints. The null hypothesis for each endpoint is that the two treatment groups do not differ in their hazard

rates. The alternative hypothesis is that the intervention group on lithium has a lower hazard rate than the placebo group. As with the primary analysis, log-rank test and Cox proportional hazards models will be used.

For secondary objective#2, the null hypothesis for each of the factors is that treatment effect does not differ over levels of the factor. The alternative hypothesis is that there is differential treatment effect over levels of the factor. Effect modification will be evaluated through regression methods. Cox proportional hazards regression model will include the treatment term, a term for the target factor, and the interaction term of the two. If the null hypothesis is rejected at $p=0.05$ level, i.e., the interaction term in the model is statistically significant, separate regression models will be refitted for each level of the factor. A forest plot will be used to display the results.

For secondary objective#3, the null hypothesis is that total event rates do not differ by treatment assignment, and the alternative hypothesis is that there is a difference in total event rates across treatment groups. We will use Generalize Linear Models (glm), namely Poisson regression, to model cumulative total of endpoint events with an offset for follow up time.

For secondary objective#4, the null hypothesis is that change in symptoms and suicidal ideation in the lithium group is similar to that of the placebo group. The alternative hypothesis is that there is a difference in change across treatment groups over time. We will use Generalize Linear Models (glm), namely Logistic regression, to model presence or absence of symptoms and suicidal ideation at each follow up visit, while allowing for random effects of variation in symptoms of bipolar disorder and depression at baseline.

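### Trait impulsivity and trait aggression, measured on 30- and 29-item baseline scales, are to be tested as moderators in two groups with no stated cut-off; a continuous-score interaction would usually keep more information

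*SAP*

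**What the plan says.** Protocol Section VI (Covariates) states: "Measures of potential effect modifiers will include traits of impulsivity and aggression". Protocol Table 1 lists both instruments under moderators: a 30-item scale described as "Impulsivity as a trait" and a 29-item scale described as "Aggression as a trait". Table 6 schedules each once, at baseline.

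The analysis plan turns both into two groups. SAP 5.1, objective 2(e) and (f), names "individuals with and without trait impulsivity" and "individuals with and without trait aggression". The protocol's secondary objective (b), items 5 and 6, is worded the same way.

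SAP 5.3 gives the method: "Cox proportional hazards regression model will include the treatment term, a term for the target factor, and the interaction term of the two". If that interaction reaches p=0.05, "separate regression models will be refitted for each level of the factor", and a forest plot displays the results.

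SAP 5.2 defines the outcome for objective 2 but not the moderator groups. No score threshold, quantile rule or continuous-score analysis for either scale appears in either document.

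**The concern.** A two-group analysis of a multi-item score needs a cut, and the plan does not give one. Two things follow. First, grouping a graded score usually discards information about how the treatment effect changes along it, in an analysis that already has few events for an interaction. Second, the answer depends on where the cut falls, and the p=0.05 rule lets that choice decide whether per-level models are fitted at all.

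The gap is specific to these scales. For impulsive versus non-impulsive attempts the plan does give an operational rule: protocol Section VI uses absence of premeditation on the Suicide Intent Scale, and SAP 5.2 names the item. At stake is how informative and reproducible two named moderator analyses will be. The trial's main conclusion is not at stake.

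**Working it through.** **Inputs from the documents.** 745 evaluable patients per arm; 1-year event rates of 15% and 9.45%; 182 events and 90% power (SAP 10 and Table 2); final two-sided alpha 0.048 for the primary test (SAP 10); interaction level 0.05 (SAP 5.3), taken here as two-sided.

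**Plan's own figure.** Events = 745 × 0.15 + 745 × 0.0945 = 182.2. HR = ln(1 − 0.0945)/ln(1 − 0.15) = 0.611. By Freedman's formula, √182 × (1 − 0.611)/(1 + 0.611) = 3.26. Subtracting the critical value 1.977 for alpha 0.048 leaves 1.28, which is 90.0% power. The design figure reproduces. The documents give no power figure for the moderator analyses, so 182 is used only as the number of events available to them.

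**Assumptions not in the documents.** Roughly normal scores; an interaction linear in the log hazard, of size b per SD; b varied from 0.1 to 0.5.

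**Information kept by a split.** If a share p is classed as having the trait, with cut c on the standard normal scale, the fraction kept relative to the continuous score is φ(c)²/[p(1 − p)].
- Median split: 0.3989²/0.25 = 0.637, equivalent to about 116 of 182 events.
- Upper-quartile split: 0.3178²/0.1875 = 0.539, equivalent to about 98 events.

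These fractions do not depend on b.

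**Power.** SE(interaction) = 2/√(182 × var(x)), and power ≈ Φ(z − 1.96). At b = 0.3:
- Continuous score per SD: SE = 2/√182 = 0.148; z = 0.3/0.148 = 2.02.
- Median split: expected difference between groups 2 × 0.798 × 0.3 = 0.479; SE = 4/√182 = 0.297; z = 1.61.
- Upper-quartile split: z = 2.02 × √0.539 = 1.49.

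| b (log-HR per SD) | Continuous | Median split | Upper-quartile split |
|---|---|---|---|
| 0.1 | 10% | 8% | 8% |
| 0.2 | 27% | 19% | 17% |
| 0.3 | 53% | 36% | 32% |
| 0.4 | 77% | 58% | 51% |
| 0.5 | 92% | 77% | 70% |

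The SE formula treats events as evenly divided between arms. With the planned 112 and 70 events, √(1/112 + 1/70) = 0.152 replaces 0.148. This scales all three SEs alike and leaves the comparison unchanged.

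**Reversed case.** Suppose the true modification is a step of 0.6 log-HR at the median. The median split then has z = 0.6/0.297 = 2.02, or 53% power. The linear score has z = 2.02 × 0.798 = 1.61, about 36%. The arithmetic is the same with the roles exchanged.

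**The case against.** The strongest reply is that the SAP already limits the weight of these results: "Analyses for these objectives are exploratory in nature and as such, they are not statistically powered for formal hypothesis testing". That stands, and it caps the importance of the point. It does not supply the missing definition, and the SAP still attaches a p=0.05 decision rule to the test.

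A second reply is that the model in SAP 5.3 could take a continuous term. That is true of the interaction model. The two-group wording of the objective and the refit by level do not fit a continuous score.

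A third is that the gain from a continuous score depends on the shape of the modification. This also stands, as the reversed case shows. The continuous score is a sound default, but it is not better under every truth.

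Two stronger readings are tempting and should be resisted:
- *The cut will be picked from the outcome data.* Nothing in the documents says so. Both scores are collected at baseline, so a cut could be set blind from pooled scores, and SAP 1 requires deviations to be documented. What remains is that, with no cut stated, a late choice would not register as a deviation.
- *Impulsivity and aggression are the trial's leading hypotheses.* Protocol Section I bases the proposal on suicidality as a target symptom in its own right. It discusses impulsivity and aggression as possible mediators and calls the evidence suggestive. Section VI names the traits as potential effect modifiers without ranking them.

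**Conclusion.** The point holds as a minor improvement to an exploratory analysis. The absence of a cut-off and the reliance on discrete levels can be read directly from the documents and need no assumption.

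The size of the loss is conditional. For roughly normal scores and a log-linear interaction, a median split gives up about 36% of the interaction information and an upper-quartile split about 46%. Over the assumed effects, the absolute power loss runs from about 2 points (0.1 log-HR per SD) to about 26 points (77% against 51% at 0.4, upper quartile). At 0.3 or below, even the continuous analysis has little better than even odds of detecting modification, so the change improves the analysis without making it well powered.

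The primary test, the sample size and the primary type I error are unaffected.

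**What to change.** Before unblinding, amend SAP 5.1, objective 2(e)–(f), and SAP 5.3:
- For these two scales, make the moderator test the interaction of treatment with the continuous baseline score, per SD, with a spline check for non-linearity.
- For these two factors, replace the refit by level with the treatment hazard ratio and confidence interval at the 25th, 50th and 75th percentiles of the score, shown in the forest plot.
- If a two-group display is kept, fix one cut per scale from pooled, blinded baseline scores and use it for display only.

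The cost is SAP wording; no new data are needed. The downsides are reliance on a functional form, which the spline check addresses, and a slightly less simple presentation.
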